Prevention Point Philadelphia (PPP). PPP is the only syringe exchange in Philadelphia. They promote health, empowerment and safety for communities affected by drug use and poverty by offering case management, syringe exchange, medical services, HIV and Hepatitis C (HCV) testing, addiction services, housing services, free meals, legal clinic and overdoes prevention and reversal training. PPP serves hundreds of people throughout the week, many of whom attend almost daily.

Sampling

Subjects will be screened for their interest in and eligibility for participating. We aim to enroll 68 women, assuming a 75% retention rate at the end of the intervention, leaving us a final study sample of 50. Treatment allocation will be accomplished using randomization through REDCap, a HIPAA approved research management software.

PROCEDURE PHASE 3

For graphic representation of study Procedure, see attached. Participants will be asked to participate after or while waiting for services at the study site. If they are interested, research staff will take participants into a designated private room and ask eligibility questions and be HIPAA consented. If they report that they meet the eligibility requirements, they will be taken to an HIV tester at Prevention Point Philadelphia for confirmation of status. If a woman tests positive for HIV, she will be provided regular counseling through PPP's testing program and given access to resources and services to link her to immediate care. If the woman does not have HIV and is eligible to be in the study, she will be consented into the study.

Once confirmed to be HIV-, participants will be randomized to a group using REDCap's randomization tool and a baseline survey will be conducted by research staff. All survey assessments will be orally administered to participants to address any literacy or cognitive issues. Responses will be entered into REDCap by a research staff member.

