Participants will also continue to be monitored by the physician at Prevention Point. It is expected that a blood test or urine sample measuring PrEP levels and an HIV screening test would be done at the beginning, mid-point and the end of the intervention. It will also be done three months after the intervention is over. This will provide biomedical adherence data and ensure that participants have remained HIV negative.

After the intervention is over, all study participants may continue their PrEP prescription and have it administered out of the medical clinic at Prevention Point. In addition, PrEP counselors will remain available for participants should they have any further questions. Specialized counseling and text messages will no longer be provided. Three months after the intervention is over, we will contact participants to complete the last study assessment. This will be done at Prevention Point when the participant is there.

Instruments

There are five study assessments (See attachments). They include:

1. Eligibility Screener
2. Baseline Assessment
3. Mid-Intervention Assessment (in person and one question via text)
4. Post-Intervention Assessment
5. Three month follow-up Assessment

Analysis Plan

General - All data will be graphed and tabulated by treatment group for review of distributional properties and anomalous values prior to the main analyses. Continuous and normally distributed variables will be summarized with means and standard deviations. All parameter estimates will be bound by 95% confidence intervals and tests for differences in means and proportions will be deemed statistically significant $p < 0.05$. Post-hoc tests of significance will be based on adjustments for alpha to protect family-wise error rates at 5% using the method of Benjamini & Hochberg. For all analyses described in this study, we will use Statistical Analysis Software (SAS, version 9.4, Cary, N.C.).

Primary Outcome. The study's intent is to provide directional insight into the design of subsequent programmatic studies. As such, univariate group comparisons will be accomplished using an independent two-sample t-test for continuous measures (or non-parametric Wilcoxon

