statistic if the data is non-normally distributed) and chi-square test for categorical measures (or Fisher's Exact test if appropriate). Blood test results will also be compared to adherence benchmarks for Tenofovir-Emtricitabine and categorized as a binary variable (yes/no) based upon the mean value observed by all patients, with data at one month, three months and three months post intervention. We will use ANCOVA to assess differences between self-reported adherence and adherence as measured by blood test in the treatment group. Primary efficacy analyses will be a comparison of experimental to control group at one month, three months and three months post intervention, while other subgroup analyses based on race/ethnicity or age, for instance, as well as potential mediators and moderators, will be considered post-hoc exploratory analyses. In addition, logistic regression modeling will be used for binary adherence measures to assess group differences. Model assumptions will be tested, including linearity between the logit of the independent variables and the dependent, multicollinearity, and model misspecification.

Secondary outcomes. Secondary outcomes include self-efficacy, PrEP attitudes and decisional conflict. These measures are all continuous. Following evaluation of the primary outcome, we will explicitly examine the association between treatment adherence characteristics and extent of change among individuals in the treatment conditions in order to evaluate dose-response associations. Multiple linear models will be used to examine relationships between the groups and decisional conflict scale items, self-efficacy, and PrEP attitude scales at month three and three months post intervention. In these models, baseline outcome measures will be adjusted as covariate in the model development. PrEP attitudes will also be assessed through perceptual mapping analysis and compared from baseline to three month and three month follow-up for each group to assess "movement" toward adherence and away from negative perceptions of PrEP use. Promise of efficacy would indicate more movement by those in the "Enhanced" group compared to the "Basic" group. We will also explore potential mediators and moderators (HIV stigma, depression, level of drug use, social support). Outliers will be assessed using standardized residuals; if necessary, analyses will be accomplished for all data as well for non-outlying cases only.

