Acceptability and feasibility will be analyzed using survey items and objective measures (opened text messages, prescription pick-up). Quantitatively we will assess each feasibility and acceptability measure in both groups by inspecting trajectory plot of mean levels of satisfaction over time. No formal testing is proposed except for the descriptive statistics summarized at each follow-up assessment. We will also explore associations between participant characteristics and acceptability in order to identify subgroups of participants for whom the intervention may be less acceptable. Qualitative data will be collected via open-ended answers on the mid-intervention, post intervention and three month follow-up survey. This data will be analyzed using the Krueger method of analyzing narrative data. A thematic framework will be developed to create categories and quotes will be indexed according to categories to reduce data. Charting of quotes to enable analysis will then occur. These quotes, along with items with low mean ratings and those with the highest proportion of disagree and strongly disagree responses, will be used to assess acceptability and feasibility to inform development of a full-scale intervention.

Power calculations are not provided because we will be pilot testing a new intervention, and its effect size is not known. We have not fully powered the randomized test due to the study's size and purpose, which is to assess the feasibility, acceptability and promise of efficacy of the intervention, however with a projected n=25 in each group comparing adherence we have 80% power to detect an effect size of 0.79 (if it is a continuous measure) or an OR or 2.56 (if binary). Positive results will aid in our ability to further test the intervention in a fully powered randomized controlled trial and whether it is feasible in the context of offering it in a community-based, clinical setting.

Procedures Involved in Human Research

Description of Protocol

Consent Process

HRP-802=-Investigator Guidance Informed Consent will be followed to obtain informed consent. Before all assessments, a research staff member will review the written informed consent with the participants. Participants will have time to review the material and will be reminded that their participation is voluntary.

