Participation may contribute to increasing participants' initiation and adherence of PrEP, which will lower their HIV risk. Participation also may help participants consider how perceived stigma impacts their feelings about PrEP and help "normalize" the use of HIV prevention within the IDU community. The risks of discomfort or embarrassment discussing HIV and PrEP are reasonable in relation to the anticipated direct benefits to the subjects and the contribution subjects can make to society by reducing HIV stigma among WWIDs and encouraging HIV prevention efforts among their peers.

Privacy

As noted, all data will be coded to protect the confidentiality of participants. Only the Principal Investigator and the study coordinator will have access to the list of actual participant names and cell phone numbers. That list will be kept in a locked file (hardcopy only) in the office of [name]. The REDCap dataset with the coded data, with names removed, will be stored behind the firewall of Temple University. Medical information (adherence, HIV tests etc.) in medical charts will not be removed from Prevention Point. The study coordinator will access this through Prevention Point's electronic health record and note findings in the de-identified REDCap

database that will assign an ID number for each participant. Information will be entered into REDCap as coded data (i.e. adherence is coded 0 as no, 1 as yes). The PrEP counselors will know the names of the participants, but they will not have access to the REDCap database or participant medical records. The research assistant will only have access to de-identified data.

Compensation

Participants will receive up to a total of \$175 in gift cards. These incentives will be provided for different steps of the research study. Compensation will not be provided to those who drop out of the study or do not complete the step. Compensation will be broken down as follows:

- \$5 for conducting the eligibility screener and HIV test
- \$15 for completing the baseline test
- \$40 for meeting with the PrEP counselor (Up to four times, \$10 each time)
- \$15 for doctor visits (three times, \$5 each time)
- \$10 for completing one-month survey
- \$20 for completing three month survey
- \$50 for completing three month follow up survey
- \$20 for cell phone minutes

References

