enable analysis will then occur. These quotes, along with items with low mean ratings and those with the highest proportion of disagree and strongly disagree responses, will be used to assess acceptability and feasibility to inform development of a full-scale intervention.

Power calculations are not provided because we will be pilot testing a new intervention, and its effect size is not known. We have not fully powered the randomized test due to the study's size and purpose, which is to assess the feasibility, acceptability and promise of efficacy of the intervention, however with a projected n=25 in each group comparing adherence we have 80% power to detect an effect size of 0.79 (if it is a continuous measure) or an OR of 2.56 (if binary). Positive results will aid in our ability to further test the intervention in a fully powered randomized controlled trial and whether it is feasible in the context of offering it in a community-based, clinical setting.

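### The stated 80% power for an odds ratio of 2.56 with 25 women per group cannot be reached: two-sided power is at most about 42%, whatever the control adherence rate

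*Combined protocol and SAP*

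**What the plan says.** The last paragraph of the protocol's Analysis Plan first says that no power calculation is provided and that the pilot is not fully powered. It then makes a specific claim: "with a projected n=25 in each group comparing adherence", the study has "80% power to detect an effect size of 0.79 (if it is a continuous measure) or an OR or 2.56 (if binary". The closing paragraph of the SAP (Statistical Analysis Plan - Aim 3 Clinical Trial) makes the same claim: "80% power to detect an effect size of 0.79 (if it is a continuous measure) or an OR of 2.56 (if binary". Neither gives a control adherence rate, a test or a sidedness for it.

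The 25 per group comes from the protocol's Sampling section: 68 enrolled, "assuming a 75% retention rate at the end of the intervention, leaving us a final study sample of 50".

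Binary adherence is a planned primary measure. Under Primary Outcome, both documents dichotomise the blood-test results, name the chi-square test (or Fisher's exact) for categorical measures, and add that "logistic regression modeling will be used for binary adherence measures to assess group differences". The protocol's Privacy section says that in the database "adherence is coded 0 as no, 1 as yes". The General paragraph sets the criterion: "tests for differences in means and proportions will be deemed statistically significant" at p < 0.05, with 95% confidence intervals.

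**The concern.** With 25 per group, an odds ratio of 2.56 is a modest effect: at best a contrast of about 38% against 62%. Two groups of that size do not usually separate such rates with 80% power. The two halves of the sentence also disagree. On the usual logistic scaling, a standardised difference of 0.79 corresponds to an odds ratio of exp(0.79 × π/√3) = 4.2, not 2.56, yet both are presented as detectable with the same sample and power.

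The odds ratio is the only statement of sensitivity for the yes/no form of the primary outcome. A reader who trusts it would take a non-significant pilot result as fair evidence against an odds ratio of 2.56. The same reader could carry 2.56 forward as a realistic detectable effect when planning the full-scale trial that the paragraph anticipates.

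**Working it through.** **Inputs.** From the documents: n = 25 per group, stated power 80%, stated effects 0.79 and odds ratio 2.56, significance at p < 0.05. Assumed, because not stated: two-sided testing (one-sided is also tried) and the control adherence rate p₁, varied from 2% to 98%.

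**1. The continuous figure reproduces.** Detectable difference = (1.96 + 0.8416) × √(2/25) = 0.792, as stated. The exact t-test value is 0.809, a trivial gap. So two-sided 5%, 80% power and 25 per group are the settings behind that half of the sentence.

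**2. The binary figure, best case by hand.** For odds ratio OR, p₂ = OR·p₁ / (1 − p₁ + OR·p₁). Power by normal approximation with pooled null variance, where p̄ = (p₁ + p₂)/2, is

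Φ{ [ (p₂ − p₁) − 1.96·√(2p̄(1 − p̄)/n) ] / √( [p₁(1 − p₁) + p₂(1 − p₂)]/n ) }.

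Power is highest at p₁ = 0.385, where p₂ = 0.616 and the difference is 0.231. The critical difference is 1.96 × √(2 × 0.5 × 0.5/25) = 0.277, and the standard error under the alternative is 0.138. Power = Φ((0.231 − 0.277)/0.138) = Φ(−0.337) = 36.8%. Even in the best case, the true difference is smaller than the difference needed for significance.

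**3. Over control rates, and by exact enumeration of all 26 × 26 outcomes.** Power at odds ratio 2.56, two-sided 5%:

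| Control rate (assumed) | Enhanced rate | Normal approx. | Exact chi-square | Fisher |
|---|---|---|---|---|
| 10% | 22.1% | 21% | 22% | 12% |
| 20% | 39.0% | 31% | 33% | 21% |
| 30% | 52.3% | 36% | 40% | 29% |
| 38.5% | 61.6% | 37% | 42% | 31% |
| 50% | 71.9% | 35% | 39% | 28% |
| 60% | 79.3% | 31% | 33% | 21% |
| 70% | 85.7% | 26% | 28% | 17% |

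The logistic Wald test peaks at 36.6% asymptotically, or 36.2% by enumeration. The logistic likelihood-ratio test peaks at 42%, like chi-square.

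**4. More generous settings.** One-sided 5%: at most 49.5% (normal approximation) or 53.6% (exact chi-square). All 68 women retained, 34 per group, two-sided: at most 47.7% (normal approximation) or 49.3% (exact likelihood-ratio).

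**5. What 25 per group can detect with 80% power (two-sided odds ratio):**

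| Control rate (assumed) | Normal approx. | Exact chi-square | Fisher |
|---|---|---|---|
| 20% | 5.5 | 5.2 | 6.1 |
| 30% | 5.1 | 4.7 | 5.7 |
| 40% | 5.3 | 5.0 | 6.2 |
| 50% | 6.2 | 5.8 | 8.0 |

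The minimum over all control rates is 5.1, 4.7 and 5.7 respectively, each near a 30% control rate.

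**6. What an odds ratio of 2.56 would need.** By normal approximation, 73 per group at the most favourable control rate and 143 at a 10% control rate, the largest value between 10% and 70%. That is about three to six times the projected 25.

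**7. Precision.** In the best case (38.5% control), SE of the log odds ratio = √[1/(25 × 0.385 × 0.615) + 1/(25 × 0.616 × 0.384)] = 0.581. The expected 95% interval is exp(0.940 ± 1.96 × 0.581) = 0.82 to 8.00.

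**The case against.** The strongest reply is that the figure does little work. The paragraph disclaims a power calculation, the stated intent is directional insight, 68 comes from retention to 50, and no stopping or progression rule uses 2.56. That stands and limits the harm. It does not make the number true, because the text moves from the disclaimer to a definite claim of 80% power.

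A second reply is that 2.56 may be mislabelled. Read as a risk ratio at a control rate near 25%, it gives 81% power. It also fits an odds ratio per standard deviation of a continuous covariate, with 50 women and an event rate near 23%. Pooling three time points as if independent (75 per group) gives 81% as well. None of these is what the text says: it names an odds ratio with 25 in each group, and the primary analysis compares groups at each time point. They are a good reason to ask for the source calculation.

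Third, the 42% ceiling belongs to the uncorrected chi-square test, whose actual type I error at this size reaches about 6.5%. That is correct, and it makes 42% generous: Fisher's exact test gives 31%. The size of the overstatement also depends on sidedness: 80/42 = 1.9 or more two-sided, but 80/53.6 = 1.5 one-sided.

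**Conclusion.** The binary power statement is wrong as written in both documents. With 25 women per group, power for an odds ratio of 2.56 is at most about 42% two-sided, against the stated 80%. If the true odds ratio were 2.56, the planned two-sided test would therefore miss it at least 58% of the time. The ceiling needs no assumed control rate, because it is the maximum over the whole range. It does assume two-sided testing, which fits the 95% intervals and the reproduced 0.79; one-sided testing still falls well short. The detectable odds ratios of 4.7 to 5.8 (chi-square) or 5.7 to 8.0 (Fisher) do rest on an assumed control rate of 20-50%. If splitting blood results at the overall mean puts about half the women in each category, the rates lie near the best case, and power for 2.56 is still only 31-42%. The continuous figure and the enrolment target are unaffected.

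**What to change.** Ask the sponsor for the calculation behind 2.56. Unless it shows a different quantity that can be correctly labelled, replace the binary clause in the protocol's power paragraph and in the SAP's, for example with:

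> or, if binary, an odds ratio of about 5 to 6 for an assumed control adherence of 20-50% (two-sided 5% chi-square test, exact power; for example 30% vs 69%, or 50% vs 86%). Power for an odds ratio of 2.56 is at most about 42%.

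The two examples have exact chi-square power of 84% and 82%. Under Fisher's exact test they have 76% and 71%, so if Fisher is the intended test, quote 5.7 to 8.0 and a ceiling of 31% instead. Use one method throughout, name the test and its sidedness, and label the control rate as an assumption. Leave 0.79 as it is.

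The cost is one sentence in each document. Enrolment, conduct and analysis do not change; the stated sensitivity becomes less favourable.

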G- END OF INTERVENTION SURVEY

H- THREE MONTH FOLLOW UP SURVEY

I – OUTCOMES AND SOURCE

Statistical Analysis Plan - Aim 3 Clinical Trial

General. All data will be graphed and tabulated by treatment group for review of distributional properties and anomalous values prior to the main analyses. Continuous and normally distributed variables will be summarized with means and standard deviations. All parameter estimates will be bound by 95% confidence intervals and tests for differences in means and proportions will be deemed statistically significant $p < 0.05$. Post-hoc tests of significance will be based on adjustments for alpha to protect family-wise error rates at 5% using the method of Benjamini & Hochberg. For all analyses described in this study, we will use Statistical Analysis Software (SAS, version 9.4,Cary, N.C.).

Primary Outcome. The study's intent is to provide directional insight into the design of subsequent programmatic studies. As such, univariate group comparisons will be accomplished using an independent two-sample t-test for continuous measures (or non-parametric Wilcoxon statistic if the data is non-normally distributed) and chi-square test for categorical measures (or Fisher's Exact test if appropriate). Blood test results will also be compared to adherence benchmarks for Tenofovir-Emtricitabine and categorized as a binary variable (yes/no) based upon the mean value observed by all patients, with data at one month, three months and three months post intervention. We will use ANCOVA to assess differences between self-reported adherence and adherence as measured by blood test in the treatment group. Primary efficacy analyses will be a comparison of experimental to control group at one month, three months and three months post intervention, while other subgroup analyses based on race/ethnicity or age, for instance, as well as potential mediators and moderators, will be considered post-hoc exploratory analyses. In addition, logistic regression modeling will be used for binary adherence measures to assess group differences. Model assumptions will be tested, including linearity between the logit of the independent variables and the dependent, multicollinearity, and model misspecification.

Secondary outcomes. Secondary outcomes include self-efficacy, PrEP attitudes and decisional conflict. These measures are all continuous. Following evaluation of the primary outcome, we will explicitly examine the association between treatment adherence characteristics and extent of change among individuals in the treatment conditions in order to evaluate dose-response associations. Multiple linear models will be used to examine relationships between the groups and decisional conflict scale items, self-efficacy, and PrEP attitude scales at month three and three months post intervention. In these models, baseline outcome measures will be adjusted as covariate in the model development. PrEP attitudes will also be assessed through perceptual mapping analysis and compared from baseline to three month and three month follow-up for each group to assess "movement" toward adherence and away from negative perceptions of PrEP use. Promise of efficacy would indicate more movement by those in the "Enhanced" group compared to the "Basic" group. We will also explore potential mediators and moderators (HIV stigma, depression, level of drug use, social support). Outliers will be assessed using standardized residuals; if necessary, analyses will be accomplished for all data as well for non-outlying cases only.

Acceptability and feasibility will be analyzed using survey items and objective measures (opened text messages, prescription pick-up). Quantitatively we will assess each feasibility and acceptability measure in both groups by inspecting trajectory plot of mean levels of satisfaction over time. No formal testing is proposed except for the descriptive statistics summarized at each follow-up assessment. We will also explore associations between participant characteristics and acceptability in order to identify subgroups of participants for whom the intervention may be less acceptable. Qualitative data will be collected via open-ended answers on the mid-intervention, post intervention and three month follow-up survey. This data will be analyzed using the Krueger method of analyzing narrative data. A thematic framework will be developed to create categories and quotes will be indexed according to categories to reduce data. Charting of quotes to

enable analysis will then occur. These quotes, along with items with low mean ratings and those with the highest proportion of disagree and strongly disagree responses, will be used to assess acceptability and feasibility to inform development of a full-scale intervention.

Power calculations are not provided because we will be pilot testing a new intervention, and its effect size is not known. We have not fully powered the randomized test due to the study's size and purpose, which is to assess the feasibility, acceptability and promise of efficacy of the intervention, however with a projected n=25 in each group comparing adherence we have 80% power to detect an effect size of 0.79 (if it is a continuous measure) or an OR of 2.56 (if binary). Positive results will aid in our ability to further test the intervention in a fully powered randomized controlled trial and whether it is feasible in the context of offering it in a community-based, clinical setting.

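### The plan says Benjamini-Hochberg protects the family-wise error rate at 5% for post-hoc tests, but that method controls the false discovery rate (minor)

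*Combined protocol and SAP*

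**What the plan says.** The same sentence appears in the General paragraph of the protocol's Analysis Plan and of the Statistical Analysis Plan - Aim 3 Clinical Trial. Post-hoc tests are to use "adjustments for alpha to protect family-wise error rates at 5% using the method of Benjamini & Hochberg". Neither document mentions the false discovery rate or names another multiplicity method.

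The Primary Outcome paragraph shows what counts as post-hoc: "subgroup analyses based on race/ethnicity or age, for instance, as well as potential mediators and moderators, will be considered post-hoc exploratory analyses". The primary group comparisons at the three follow-up times are set apart from these, so the adjustment sentence does not cover them.

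Six factors are named. Race/ethnicity and age are given as examples under Primary Outcome. HIV stigma, depression, level of drug use and social support are listed under Secondary outcomes. The number of tests in the family is not stated. The power statement works "with a projected n=25 in each group".

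**The concern.** The sentence promises one error rate and names a method built for another. The family-wise error rate is the chance of at least one false positive in the set of tests. The false discovery rate is the expected share of false positives among the results declared significant. The two agree when every null hypothesis is true, because any rejection is then false. They separate once some effects are real: each correct rejection makes the Benjamini-Hochberg threshold for the remaining tests more lenient.

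As written, an analyst cannot always deliver the stated property with the stated method. A reader would credit the subgroup and moderator findings with a 5% family-wise guarantee they do not have. Those findings may feed the design of the later, fully powered trial. Because the two routes can declare different results significant, the mismatch also leaves a choice open after the data are seen.

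**Working it through.** **Inputs from the documents:** nominal level 5%; the method named in the General paragraph; 25 per group. **Assumptions, because the documents give no values:** two-sided tests, number of tests *m*, share of tests with a real effect, size of those effects, and correlation between tests.

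**1. The stated 5%, with no real effects.** For 6 to 20 tests, simulated family-wise error under Benjamini-Hochberg is 4.9-5.0% if the tests are independent and 4.0-4.5% at correlation 0.5. The stated figure holds in this case.

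**2. A hand-checkable counterexample.** Take three independent tests, one with an effect so large that it is always detected and two true nulls. The Benjamini-Hochberg cut-offs for the second and third ordered p-values are 2/3 × 0.05 = 1/30 and 0.05. A false positive occurs if either null p-value is at or below 1/30, or if both lie between 1/30 and 1/20:

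- 1 − (29/30)² = 59/900 = 0.0656
- (1/20 − 1/30)² = (1/60)² = 0.0003
- Sum: 0.0658, or 6.6%

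Simulation of this case also gives 6.6%. Holm gives 5.0%. The 5% guarantee therefore fails with as few as three tests.

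**3. A range of cases.** Two-sided z-tests at 0.05, equicorrelated normal statistics, 200,000 draws per case. The Monte Carlo standard error near 5% is √(0.05 × 0.95 / 200,000), about 0.05 points. Noncentrality 2.8 = 1.96 + 0.84 corresponds to 80% power for a single unadjusted test. Family-wise error of Benjamini-Hochberg with half the tests non-null:

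| Noncentrality | Independent, 6 / 10 / 20 tests | Correlation 0.5, 6 / 10 / 20 tests |
|---|---|---|
| 0.7 | 2.9 / 2.9 / 3.1% | 3.3 / 3.6 / 3.7% |
| 1.4 | 3.8 / 4.2 / 5.0% | 4.4 / 5.0 / 6.2% |
| 2.8 | 7.6 / 10.9 / 17.9% | 6.2 / 7.7 / 10.8% |

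With one real effect at 2.8, the family-wise error is about 7% if independent and 5.3-5.7% at correlation 0.5. With one at 1.4, it is 4.8-5.1% and 4.4-4.7%.

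**4. What these noncentralities mean here.** For a continuous outcome and a factor that splits each group of 25 evenly (12.5 per cell), in standard deviation units:

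- Within-subgroup effect = noncentrality × √(2/12.5) = noncentrality × 0.40, giving 0.28 / 0.56 / 1.12 for 0.7 / 1.4 / 2.8.
- Interaction = noncentrality × √(4/12.5) = noncentrality × 0.566, giving 0.40 / 0.79 / 1.58.

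The plan gives 0.79 as the whole-group effect it can detect. In the cases run, interactions up to that size leave family-wise error at or below 6.2%. The 2.8 row needs interactions twice as large.

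**5. Comparators.** In the same cases the false discovery rate of Benjamini-Hochberg does not exceed 5% beyond simulation error (2.0-2.6% with half the tests non-null), and Holm's family-wise error does not exceed 5%. Each method delivers its own error rate.

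**The case against.** The strongest reply is that almost nothing turns on this. The tests are exploratory, the study seeks only directional insight, and Benjamini-Hochberg does hold family-wise error near 5% when nothing is going on. On that view the sentence is imprecise rather than baseless. This stands, and it is why the point is rated minor.

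Several objections to the figures also stand in part:

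- The family size and the share of real effects are assumed, and the named list of factors is open-ended.
- The effect-size translation fits a balanced binary factor and a continuous outcome. It does not describe mediation tests, continuous moderators or a binary adherence outcome.
- The z-tests ignore the conservatism of Fisher's exact test in small cells, so the error may be overstated for binary adherence.
- A modest excess does not need many effects, since one strong effect already gives about 7% under independence. Only the double-digit figures need many strong ones.

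The authors may have meant Hochberg's step-up procedure, which controls family-wise error under independence or suitable positive dependence. Both places name Benjamini & Hochberg, however, so intent cannot be settled from the text. None of these objections makes the sentence correct.

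**Conclusion.** The concern holds and is minor. The plan attributes to Benjamini-Hochberg a 5% family-wise guarantee that it does not provide, in two places, with no correcting text. That conclusion rests on the definition of the method and on the exact three-test example, not on the simulated scenarios.

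The size of the excess does rest on assumptions. For moderate effects it is small or absent. It reaches double figures only with ten or more tests, half of them carrying effects that seem unlikely to be common in a pilot of this size. The primary comparisons, sample size and power statement are unaffected.

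**What to change.** Change one phrase in the General paragraph of both the protocol's Analysis Plan and the SAP. There are two options:

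- **State the rate the method controls**, for example: *post-hoc tests will control the false discovery rate at 5% (Benjamini-Hochberg)*. This suits exploratory work and changes no analysis. The cost is that no family-wise claim can be made for these tests.
- **Keep the 5% family-wise claim and replace the method with Holm.** This costs power. With half the tests non-null and independent, average power per real effect for 6 / 10 / 20 tests falls from 68 / 67 / 66% to 60 / 53 / 44% at noncentrality 2.8, and from 13 / 10 / 8% to 11 / 8 / 5% at 1.4.

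The first option is preferable here. If Hochberg's step-up procedure was intended, the text should name it and its dependence condition. In the same edit, add a line listing which post-hoc tests form the family, since neither error rate has a clear meaning without it.
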